9.3	CASE REPORT FORMS	22
9.4	RECORDS RETENTION	23
10	STUDY MONITORING, AUDITING, AND INSPECTING	23
10.1	STUDY MONITORING PLAN	23
10.2	AUDITING AND INSPECTING	383
11	ETHICAL CONSIDERATIONS	38
12	STUDY FINANCES	394
12.1	FUNDING SOURCE	394
13	PUBLICATION PLAN	394
14	REFERENCES	24
15	ATTACHMENTS	26 ERROR! BOOKMARK NOT DEFINED.

LIST OF ABBREVIATIONS

AE	Adverse Event/Adverse Experience
CFR	Code of Federal Regulations
CRF	Case Report Form
DSMB	Data and Safety Monitoring Board
FDA	Food and Drug Administration
GCP	Good Clinical Practice
HIPAA	Health Insurance Portability and Accountability Act
ICU	Intensive Care Unit
IDE	Investigational Device Exemption
IRB	Institutional Review Board
NS	Nanopore Sequencing
PHI	Protected Health Information
PI	Principal Investigator
SAE	Serious Adverse Event/Serious Adverse Experience
SOP	Standard Operating Procedure
SSI	Surgical Site Infection
TRAG	Tissue Request Acquisition Group
UADE	Unanticipated Adverse Device Effect

Study Summary

Title	“Answers in Hours” A Randomized Controlled Trial Using Microbiome Metagenomics for Bile Duct Cultures
Running Title	“Answers in Hours”
IRB Protocol Number	21-004234
Phase	Pilot
Methodology	Randomized 1:1 Controlled Trial
Overall Study Duration	3 years
Subject Participation Duration	90 days
Objectives	
Reduce the rate of bacterobilia driven surgical site infection (SSI) in patients undergoing pancreatic head resection by providing surgical team with Oxford Nanopore (ONT) microbial sequencing data in the post-operative setting.
 
Reduce cost of care through reduction in SSI and improved antibiotic stewardship.

Number of Subjects	140
Diagnosis and Main Inclusion Criteria	Any adult, male or female, over age 18, undergoing pancreaticoduodenectomy or total pancreatectomy for benign or malignant indication.
Study Device	GridION Sequencing Instrument
Reference therapy	Standard culture techniques and prolonged peri-operative antibiotics
Statistical Methodology	For continuous variables, t-test will be performed and for binary variables chi-square or fisher's exact testing will be performed as appropriate. Universal and multivariable linear regression adjustment will be performed if any baseline imbalances in demographic or clinical variables are detected

1 Introduction

This document is a protocol for a human research study. This study will be carried out in accordance with the procedures described in this protocol, applicable United States government regulations and Mayo Clinic policies and procedures.

1.1 Background

Postoperative infections, specifically surgical-site infections (SSI), are a significant source of morbidity in patients undergoing pancreatic head resection and have been reported in over 25% of patients^{1,2}. Infectious complications significantly increase the risk of delayed gastric emptying, pancreatic fistula, biliary fistula, abdominal collection, sepsis, acute respiratory failure, pulmonary complications, cardiovascular complications, and mortality³⁻⁵. Patients who develop SSI are also less likely to receive adjuvant chemotherapy, more likely to experience delays in adjuvant therapy, and have reduced overall survival⁶⁻⁹. Overall, complications arising from SSIs have been shown to have a direct effect on mortality, varying from 33% to 77% increased risk of mortality¹⁰, and 75% of SSI-associated deaths are directly attributable to the SSI¹¹⁻¹³.

The increased rates of morbidity and mortality associated with SSI have led to the current surgical perioperative antibiotic prophylaxis guidelines developed jointly by the American Society of Health-System Pharmacists, the Infectious Diseases Society of America, the Surgical Infection Society, and the Society for Healthcare Epidemiology of America which recommend the administration of cefazolin, cefoxitin, cefotetan, ceftriaxone, ampicillin-sulbactam, clindamycin/ vancomycin + aminoglycoside or aztreonam or fluoroquinolone, or metronidazole + aminoglycoside or fluoroquinolone 60 – 120 minutes prior to surgical incision to reduce the risk of SSI during pancreatic/ biliary tract surgeries¹⁴. This has led to extensive 'blind' use of broad-spectrum antibiotics which are associated with their own risks. Excessive usage of broad-spectrum antibiotics contributes towards the emergence of antimicrobial resistance (AMR), and their usage has been associated with acute adverse events¹⁵, and increased risk of developing sepsis¹⁶, cancer¹⁷⁻²⁰, and heart disease²¹⁻²⁴, as well as other antibiotic associated complications such as *Clostridium difficile* infections²⁵⁻²⁸.

Many patients who undergo pancreatic head resection have obstructive jaundice prior to surgery due to compression or occlusion of the common bile duct. To alleviate these symptoms, patients often undergo preoperative biliary drainage, most commonly by insertion of a biliary stent. This creates a conduit between the biliary tree and the intestinal lumen, resulting in translocation of intestinal microbes into the normally sterile bile duct systems. Numerous studies have demonstrated and confirmed an association between preoperative biliary stenting and the occurrence of SSI^{3,6-8,29}, and as such, some institutions have opted to administer postoperative antibiotics^{30-32,32-35}. In some cases, postoperative administration of broad-spectrum prophylactic antibiotics is performed without any assessment of the microbes present or sensitivities, largely due to the lack of available microbial testing infrastructure, large-volume, and nearby testing labs. In others, detection and characterization of biliary microbial contamination is currently achieved by performing standard bile cultures and

antimicrobial susceptibility testing (AST) on diverse polymicrobial community. Standard bile cultures, however, can take days to weeks to yield actionable results^{36,37} and are typically received over the course of 2 – 4 days. Bile cultures are often polymicrobial, a mixture of anaerobic and aerobic species, carry multiple antimicrobial resistant (AMR) phenotypes, and contain fungal species^{38–41}. This contributes towards delays in timely results as aerobic cultures (up to 5 days to complete), anaerobic cultures (up to 14 days to complete), and fungal cultures (up to 24 days to complete) must be performed, and additional testing must be carried out to determine the different microbial species present in the sample before AST can be carried out. Results are often generated over the course of several days, and this temporal separation between the initial broad-spectrum treatment and the acquisition of all the diagnostic information often results in uncertainty and the administration of multiple empiric antimicrobials⁴².

At our institute the current standardized approach is administer a perioperative prophylaxis course of ceftriaxone plus metronidazole 60 minutes prior to surgery (Figure 1). Antibiotic treatment is continued for 5-days postoperatively for patients undergoing pancreatic head resection, and the selection and duration of this specific broad-spectrum prophylactic regimen is based on recommended surgical guidelines and our own historical SSI culture data⁴³. During surgery, bile swab and aspirate samples are collected and transferred to the Pathology lab to undergo standard bile cultures and AST. If the bile cultures are eventually negative for microbial growth, the patient will be taken off the broad-spectrum antibiotics following completion of the 5-day prophylactic regimen (Figure 1). If the bile cultures are positive, then antibiotic treatment will be extended for 10 days, and therapy is tailored based on organisms and resistances identified in the bile cultures (Figure 1). Introduction of this approach in 2014 resulted in significant decrease in hospital stay, reduced the need for interventional radiology procedures, and decreased the risk of postoperative pancreatic fistula grade⁴³. Within the first year of introduction, our approach significantly decreased inpatient cost of care, decreased the total 30-day costs, and saved a total of \$1.1 million, in addition to improving patient outcome⁴³.

[figure not shown]

Figure 1: Schematic diagram of the current standardized perioperative prophylactic antibiotic treatment plan for patients undergoing total pancreatectomy and pancreaticoduodenectomy at our institution.

Since the introduction of our standardized approach, we have improved antibiotic tailoring by developing methods of increasing detection of anaerobic species through our use of bile aspirate in addition to collection of bile swabs³⁸. However, similar to other institutions, it takes an average of 4 days for final bacterial culture results to be generated⁴⁴, and the majority of cultured microbial species have been found to exhibit multi-resistance phenotypes. This means that for the first 4-days post-surgery many of our patients at risk of developing SSI are receiving suboptimal antimicrobial therapy. This provides potential pathogens a window of opportunity to grow and propagate prior to introduction of tailored antimicrobial therapy. Rapid methods of detecting microbial species and antimicrobial resistance phenotypes are required to shorten this window of opportunity. Our data shows that in patients with positive bile cultures it took an average of 7 days to complete microbial identification and AST for bacterial and fungal species (range = 3 – 24 days), and it took 24 days to confirm the absence of biliary microbes (5 days for aerobic cultures, 14 days for anaerobic cultures, 24 days for fungal cultures). In particular, delays in detecting *Candida* species, was of concern due to the increased risk of SSI in patients with biliary candidiasis⁴⁵. In our own patient cohort, 17% of patients were positive for biliary candidiasis, and the microbe was the presumptive cause of 22% of SSIs. In patients with biliary candidiasis, it took an average length of 4.6 days for fungal identification, and an additional 6 days for anti-fungal susceptibility testing to be complete. As anti-fungals are not part of the recommended perioperative prophylactic antimicrobial treatment course, it meant that during the first 2 weeks post-surgery these patients were at increased risk of SSI due to untreated biliary candidiasis.

A single diagnostic test that would enable simultaneous identification of bacterial species (aerobic, anaerobic, fastidious), fungal species, and antimicrobial resistance in an expedited

fashion would be highly advantageous. It would allow for all the microbial information to be generated in a single report, enabling the administration of optimal tailored antibiotics in the early postoperative window without the need for continuous changes to the treatment regimen as new information becomes available. It would also enable early cessation of antimicrobial prophylaxis if no microbes are detected, potentially reducing the complications associated with use of broad-spectrum antibiotics.

We hypothesized that use of metagenomic Oxford Nanopore (ONT) sequencing, a real-time method of sequencing that has been demonstrated to detect microbial species in as little as 6 hours^{42,46,47}, could be developed as a tool for rapid detection and characterization of biliary microbes. We have since developed methods of detecting intraoperative bile microbes, and have recently published the promising results of a prospective clinical trial that was performed to determine the feasibility and utility of ONT sequencing in detection of microbial species and antibiotic resistance genes using intra-operative bile from patients undergoing pancreatic head resection^{44,48}. Our preliminary data would suggest that not only is this technique feasible, but our ONT sequencing results highly correlate with traditional culture microbial identification and does so with a median time of 14 hours compared to 98 hours for traditional culture, a turnaround time improvement of 92%. Furthermore, the results of our study found that when standard cultures (SC) were negative (i.e. no further antibiotic therapy needed) the ONT perfectly correlated. This suggested that ONT could be used to identify patients with negative biliary microbes, enabling a more rapid cessation of unnecessary antimicrobial therapy in patients. This would improve antibiotic stewardship, a continual goal in surgical patient care.

Given these promising preliminary results, we aim to reduce the rate of SSI while minimizing overutilization of antibiotic therapy in patients undergoing pancreatic head resection by providing supplemental ONT data in addition to standard clinical cultures. This will provide not only an important potential diagnostic, but will also elucidate microbial communities within contaminated bile, potentially leading to improved targeted approaches in the future.

1.2 Investigational Device

The investigation device being utilized for this research study is the Oxford Nanopore Technologies (ONT) R9.4.1 flow cells and the ONT GridION MK1 Sequencing Instrument (Device number GXB03025). ONT sequencing will be performed using MinKNOW (version 21.11.7), MinKNOW Core (4.5.4), Bream (6.3.5) and Guppy (5.1.13) software. Microbial species identification will be achieved using Porechop (0.2.4), BBMap (35.85) and Centrifuge (1.0.4) software, and detection of antimicrobial resistance genes will be achieved using ResFinder 4.1 software^{49,50}. The ResFinder 4.1 tool, developed and maintained by the Center for Genomic Epidemiology (CGE), was selected following research that demonstrated it to be as reliable as standard antimicrobial susceptibility testing (broth microdilution, disc diffusion) for detecting clinically relevant AMR phenotypes⁵¹. Additionally, the tool utilizes a database of horizontally acquired chromosomal gene mutations that confer AMR, and thus use of ResFinder 4.1 will enable us to link predicted AMR phenotypes to specific microbial species.

To ensure that no potential resistance phenotypes are missed we will also use the PlasmidFinder (2.0.1)⁵² and CARD (CARD 2020)⁵³ tools to check for any plasmid-acquired AMR phenotypes.

If there are new releases of the software prior to the trial, the software will be updated to the latest versions and all samples in the trial will be sequenced and analyzed using the same software versions.

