(Tissue Request Acquisition Group), will be requested for managing of intraoperative samples and will notify the study team of sample receipt. After collection, microbial DNA will be extracted and sequenced in preparation for reading per protocols^{44,48}. In brief, Porechop and BBMap will be used to remove adaptor sequences and low complexity reads. The filtered reads will then be aligned using Centrifuge in order to determine species identification. Bile aspirates will be declared microbial positive when 500 or more microbial reads are detected. Additionally, 50 reads per million (RPM) ratio (RPM-r), defined as $RPM-r = RPM_{sample} / RPM_{negative\ control}$, will be used as a minimum threshold to reduce biases caused by different sequencing depth and mitigate concerns regarding potential microbial contamination, as described in previous studies^{47,73,78,79}. Relative abundance of the microbial species detected will then be determined and high abundant species (species with a relative abundance greater than 1%) will then be reported to the care team. The sequenced reads will also be used to identify acquired chromosomal AMR genes and putative AMR phenotypes using ResFinder 4.1⁵¹. A minimum coverage of 95% and a minimum sequence identity of 95% will be used, and predicted phenotype and source organism of the identified AMR gene will be reported to the care team. To ensure that no potential resistance phenotypes are missed we will also use the PlasmidFinder and CARD tools with the default settings to check for any plasmid-acquired AMR phenotypes. This will be a critical step as CRE and ESBL genes are located on plasmids. However, due to these genes being located on plasmids, use of PlasmidFinder and CARD will not be used to declare presence of CRE- and/or ESBL-organisms but instead inform the Surgical Clinical Pharmacy and the Pathology laboratory about their potential presence in the patient sample.

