ONT results different from SC	Adjust and/or narrow antibiotic therapy to cover pathogens found in ONT results, excluding those deemed clinically insignificant. SC results to only be considered in the event of treatment failure with antibiotic therapy targeted towards ONT results.

Databases Used

For the analysis of our endpoints, we are relying on sequence homology for two main tasks, mainly, (1) the identification of species and (2) identification of AMR phenotypes. For species identification, we use the refseq genome database (downloaded on 12/18/2020) with all data from the following higher order taxa groups included: human, protozoa, viral, bacterial, and fungal. For the identification of AMR phenotypes, we use the ResFinder database (downloaded on 06/04/2021, version 4.1) which contains the acquired chromosomal resistance genes, ensuring we know which species is carrying a given resistance gene. For plasmid AMR gene identification, we will use the PlasmidFinder-specific database (downloaded on 7.14.2021/version 2.0.1) and the CARD data (downloaded on 07/07/21, version CARD 2020). These databases undergo regular updates since they were first developed. To ensure the analysis remains consistent throughout the study, databases will not be updated for the duration of the study. In the unlikely event that we require a software/ database update in order to run these tools (compatibility issues with future institutionally required OS update, inability to restore databases from archives after computational disaster), we will validate any newer versions of the database and/or algorithms using the data and culture gold standards from our published study and recently collected data and will only proceed if we have comparable performance in accuracy for species and AMR identification.

Patient Follow-up and Safety Monitoring

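### A match to an acquired resistance gene does not show which organism in mixed bile carries it, yet the plan says it does and reports a source organism to the care team

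*Combined protocol and SAP*

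**What the plan says.** Section 1.2 (Investigational Device) says of ResFinder that "the tool utilizes a database of horizontally acquired chromosomal gene mutations that confer AMR", and from this concludes "thus use of ResFinder 4.1 will enable us to link predicted AMR phenotypes to specific microbial species".

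Databases Used, within 2.1 General Design, says that "we are relying on sequence homology for two main tasks": identifying species and identifying resistance. It describes the ResFinder database as one "which contains the acquired chromosomal resistance genes, ensuring we know which species is carrying a given resistance gene".

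The sequencing paragraph of 2.1 General Design gives the match rule: "A minimum coverage of 95% and a minimum sequence identity of 95% will be used". It then says that "predicted phenotype and source organism of the identified AMR gene will be reported to the care team". Species are called in a step of their own, by aligning the filtered reads with Centrifuge.

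For plasmid genes the same paragraph is more cautious. PlasmidFinder and CARD hits alert pharmacy and the pathology laboratory to a possible presence, but do not declare a CRE or ESBL organism.

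On the sample itself, section 1.1 says: "Bile cultures are often polymicrobial, a mixture of anaerobic and aerobic species".

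**The concern.** The plan derives the carrier from what is in the database. A reference database describes its own entries; it does not describe the copy found in a patient's bile. A horizontally acquired gene is by definition one that can pass between organisms, so its presence in a mixed sample is compatible with more than one carrier. Sequence homology answers which gene is present. Which organism holds it needs further evidence, such as what the rest of the same read belongs to.

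Two things are at stake.

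- **The Arm 2 report to clinicians.** Tables 3 and 5 leave organisms judged clinically unimportant out of coverage. A gene attached to such an organism by mistake could be discounted along with it. In addition, only species above 1% relative abundance are reported, while no abundance floor is stated for genes. A gene from an unreported species could therefore be attached to a reported one.
- **Any organism-level comparison of predicted resistance with culture susceptibility.** Section 5.3 says that culture and sequencing results will be captured and compared. Agreement would be scored on attributions that the described method does not support.

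**Working it through.** The plan gives no figure for how often a gene is assigned to the right organism, so the check is mainly one of logic, with a count of how mixed the pilot samples were.

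**1. The stated chain, link by link**

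- Gene call: ResFinder match at 95% coverage and 95% identity. Output: gene present in the sample.
- Species call: Centrifuge alignment of the filtered reads. Output: list of species in the sample.
- Join between the two: none stated. There is no taxonomic call on the gene-bearing read, no criterion on flanking sequence, and no undetermined category.
- Report: phenotype plus source organism.

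The third link is missing from the text, and the database claim stands in its place. In a sample with one species the join is trivial. In a sample with several it is not.

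**2. How mixed the pilot bile was**

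Inputs from section 1.4: 15 of 42 patients had positive bacterial cultures only, 1 of 42 fungal only, and 16.7% both. 16.7% of 42 is 7.

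- Check against the plan's total: 15 + 1 + 7 = 23, as stated (23/42).
- Patients with positive bacterial cultures: 15 + 7 = 22.

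Standard-culture counts from Table 2: Enterococcus 17, Streptococcus 16. As a check that these are patient counts, 13/17 = 76.5% and 15/16 = 93.8%, which are the detection rates quoted in section 1.4.

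- Minimum number with both genera: 17 + 16 − 22 = 11, or 11/22 = 50%.
- Maximum: the smaller count, 16 of 22.

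Bacterial culture entries in the common-microbe part of Table 2, leaving out Candida: 6 + 17 + 3 + 11 + 1 + 1 + 16 = 55. Per patient with a positive bacterial culture: 55/22 = 2.5. This omits anaerobes and other organisms not in those rows.

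**3. Close relatives in one sample**

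On sequencing, Table 2 gives K. oxytoca 10, K. pneumoniae 7 and Klebsiella spp. 14. If the genus row includes both species, at least 10 + 7 − 14 = 3 of 14 patients (21%) had both. Culture does not force any overlap: 7 + 4 − 11 = 0. The percentage beside the 14 is printed as 0, so I take the count at face value.

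**4. What cannot be computed**

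The misassignment rate and the number of plausible carriers per gene are not in the documents. Section 1.4 reports that 81% of culture resistance phenotypes were predicted, but does not describe this as agreement on which organism carried the resistance.

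**The case against.** **The step may exist elsewhere.** Section 2.1 summarises the analysis briefly and refers to published protocols for extraction and sequencing. A long read can span both a gene and its host's chromosome, and the separation of chromosomal from plasmid genes suggests that the authors know of the problem. This stands as a limit: one can say that the step is not stated here, not that it is absent from practice. It does not rescue the two sentences, which rest the claim on database content rather than on such a step.

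**Treatment does not turn on it.** A reader might infer that Arm 2 therapy is fitted organism by organism from the resistance report, so that a wrong carrier means wrong therapy. The documents do not support that. Tables 3 and 5 have no row for a resistance gene, and for several pathogens they call for coverage of all that matter. Regimens are chosen with Surgical Clinical Pharmacy using cultures as well as sequencing, and a gene given the wrong carrier is still reported as present. Culture with susceptibility testing runs in both arms, but how far it serves as a safeguard is unclear. Tables 3 and 5 bring it in only after treatment failure, while the Arm 2 description lets it override sequencing. Those passages must be reconciled; I count that neither for nor against this point.

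**No endpoint uses it.** This is correct. The endpoints are antibiotic use, SSI, cost and timeliness, and section 6.2 defines no organism-level resistance analysis. The reads are kept (section 8.2), so a later comparison could be re-run under a stricter rule.

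**Mixed samples do not give an error rate.** Also correct. One could divide all 60 culture entries, Candida included, by all 23 culture-positive patients to get 2.6, and read it as candidate carriers per gene. That counts fungi and a fungal-only patient, and it assumes that every organism could carry every gene. The bacterial average of 2.5 is likewise not a count of carriers.

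**Conclusion.** The point holds in limited form. The plan twice claims a property that its described method does not have, and on that footing reports a source organism to clinicians, from samples where at least half of the pilot patients with positive bacterial cultures had two named genera together. It already declines to make organism calls from plasmid hits, so its treatment of ResFinder hits is inconsistent with its own caution.

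The size of the resulting error is unknown. The consequence is confined to the accuracy of the Arm 2 report and to any organism-level comparison with susceptibility testing. A reader might infer that the trial's primary result or patient treatment is compromised; nothing in the endpoints, section 6.2 or the management tables supports that.

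The conclusion rests on the text given here. If the cited protocols contain a read-level attribution rule, writing it into the plan would largely resolve the point. It does not depend on whether the ResFinder database really is limited to chromosomal genes, which cannot be checked from these documents.

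**What to change.** - Delete the inference in section 1.2 that database content links phenotype to species, and the matching assurance in Databases Used.
- State in 2.1 General Design that a source organism is named for a ResFinder match only when the gene-bearing read is itself classified to one species on sequence outside the gene and shows no plasmid match. Otherwise, report the gene as 'present, carrier not determined'.
- In any comparison with susceptibility testing, keep these two categories apart and do not score undetermined carriers as organism-level agreement.

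The cost is protocol wording plus a scripted filter on reads that are already produced and stored, using tools that the plan already names. The downside is small: some genes will be reported without a named carrier. The gene itself is still reported, and no treatment rule changes.
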